2.1.4.1 Symptomatic hypoglycemia

Symptomatic hypoglycemia will be identified as events recorded on the dedicated eCRF “Symptomatic hypoglycemia” page, and will be categorized as follows (see study protocol for further details):

Severe symptomatic hypoglycemia

Severe symptomatic hypoglycemia is an event requiring assistance of another person to actively administer carbohydrate, glucagon, or other resuscitative actions. These episodes may be associated with sufficient neuroglycopenia to induce seizure, unconsciousness, or coma. Plasma glucose measurements may not be available during such an event, but neurological recovery attributable to the restoration of plasma glucose to normal is considered sufficient evidence that the event was induced by a low plasma glucose concentration.

The definition of severe symptomatic hypoglycemia includes all episodes in which neurological impairment was severe enough to prevent self-treatment and which were thus thought to place patients at risk for injury to themselves or others.

Note that “requires assistance” means that the patient could not help himself or herself. Assisting a patient out of kindness, when assistance is not required, should not be considered a “requires assistance” incident.

Severe symptomatic hypoglycemia will be qualified as an SAE only if it fulfills SAE criteria. All events of seizure, unconsciousness, or coma must be reported as SAEs.

In the eCRF, severe symptomatic hypoglycemia is identified based on information captured in the “Symptomatic hypoglycemic event information” page as those

- ticked “Subject was Not Capable of Treating Self and Required Assistance” to the question “Countermeasure Administration” and
- ticked at least one “Yes” to the question “Symptoms”.

Documented symptomatic hypoglycemia

Documented symptomatic hypoglycemia is an event during which typical symptoms of hypoglycemia are accompanied by a measured plasma glucose concentration of ≤ 70 mg/dL (3.9 mmol/L). Clinical symptoms that are considered to result from a hypoglycemic episode can include (but are not limited to): increased sweating, nervousness, asthenia, tremor, dizziness, increased appetite, palpitations, headache, sleep disorder, confusion, seizures, unconsciousness, and coma.

In the eCRF, documented symptomatic hypoglycemia is identified based on information captured in the “Symptomatic hypoglycemic event information” page as those

- ticked “Subject Treated Self” or “Subject was Capable of Treating Self but Received Assistance” to the question “Countermeasure Administration” and
- ticked at least one “Yes” to the question “Symptoms” and
- with a measured plasma glucose value ≤ 70 mg/dL (3.9 mmol/L).

Probable symptomatic hypoglycemia

Probable symptomatic hypoglycemia is an event during which symptoms of hypoglycemia are not accompanied by a plasma glucose determination, but was presumably caused by a plasma glucose concentration less than or equal to 70 mg/dL (3.9 mmol/L); symptoms treated with oral carbohydrate without a test of plasma glucose.

In the eCRF, probable symptomatic hypoglycemia is identified based on information captured in the “Symptomatic hypoglycemic event information” page as those

- ticked “Subject Treated Self” or “Subject was Capable of Treating Self but Received Assistance” to the question “Countermeasure Administration” and
- ticked at least one “Yes” to the question “Symptoms” and
- ticked “Oral carbohydrate”, “Intravenous glucose” or “Glucagon injection” to the question “Was Any Countermeasure Given for the Hypoglycemic Event?” and
- ticked “Yes” to the question “Did this countermeasure lead a significant improvement or prompt recovery?” and
- with no plasma glucose value,

Symptomatic hypoglycemia events fulfilling the criteria of a SAE will also be recorded on AE and SAE forms in eCRF.

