The patients are requested to perform 7-point SMPG profile measurement over a single 24-hour period on 2 different days in the week before V3 (Week 0), V21 (Week 12), V28 (Week 26) and V35 (Week 52) for FRC patients- end of treatment assessment visit. The SMPG values measured for each 7-point SMPG profile will be recorded in the patient diary and transferred into the e-CRF.

On the 7-point profile days, information on times of meals and bedtime, injection time and doses of IMP should be recorded in the patient's diary and entered in the e-CRF.

SMPG during episodes of symptomatic hypoglycemia

Whenever the patient feels hypoglycemic symptoms, plasma glucose should be measured by the patient (or others, if applicable), if possible. Patients should be instructed to measure plasma glucose levels prior to the administration of glucose or carbohydrate intake whenever symptomatic hypoglycemia is suspected ([Section 10.6.1](#)), unless safety considerations necessitate immediate glucose/carbohydrate rescue prior to confirmation.

The SMPG values are to be entered in the patient's diary and entered in the e-CRF.

Further SMPG

The Investigator may decide to request more frequent self-monitoring of plasma glucose if he/she considers necessary for the patient. The SMPG values are to be entered in the patient's diary.

9.2.1.2.3.2 Glucometer, patient diaries and training

All patients are supplied with a glucometer, the corresponding supplies (lancets, test strips, etc), an instruction leaflet, and with diaries at visit V2 (Week -1) in order to perform self-measurement of plasma glucose and its recording. The patients will be instructed to bring their glucometers and patient diaries with them to each site visit.

The glucometers should be calibrated according to instructions given in the package leaflet, and the study site should also check the glucose meters regularly using the provided control solutions for data validity.

At visit V2 (Week -1) patients are trained to accurately measure plasma glucose values with the glucometer and to correctly record the values and other requested information in the patient's diaries. It is the Investigator's responsibility to explain the need to measure glucose at the times requested and to correctly record all SMPG values in the patient's diaries to patients. Training is repeated as often as necessary at the study visits.

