10.6 SAFETY INSTRUCTIONS

10.6.1 Symptomatic Hypoglycemia

Symptomatic hypoglycemia events will be categorized as follows:

Severe symptomatic hypoglycemia

Severe symptomatic hypoglycemia is an event requiring assistance of another person to actively administer carbohydrate, glucagon, or other resuscitative actions. These episodes may be associated with sufficient neuroglycopenia to induce seizure, unconsciousness or coma. Plasma glucose measurements may not be available during such an event, but neurological recovery attributable to the restoration of plasma glucose to normal is considered sufficient evidence that the event was induced by a low plasma glucose concentration.

The definition of severe symptomatic hypoglycemia includes all episodes in which neurological impairment was severe enough to prevent self-treatment and which were thus thought to place patients at risk for injury to themselves or others.

Note that “requires assistance” means that the patient could not help himself or herself. Assisting a patient out of kindness, when assistance is not required, should not be considered a “requires assistance” incident.

Severe symptomatic hypoglycemia will be qualified as an SAE only if it fulfills SAE criteria. All events of seizure, unconsciousness or coma must be reported as SAEs.

Documented symptomatic hypoglycemia

Documented symptomatic hypoglycemia is an event during which typical symptoms of hypoglycemia are accompanied by a measured plasma glucose concentration of ≤ 70 mg/dL (3.9 mmol/L).

Clinical symptoms that are considered to result from a hypoglycemic episode can include (but are not limited to): increased sweating, nervousness, asthenia, tremor, dizziness, increased appetite, palpitations, headache, sleep disorder, confusion, seizures, unconsciousness, and coma.

Probable symptomatic hypoglycemia

Probable symptomatic hypoglycemia is an event during which symptoms of hypoglycemia are not accompanied by a plasma glucose determination, but was presumably caused by a plasma glucose concentration less than or equal to 70 mg/dL (3.9 mmol/L); symptoms improved with oral carbohydrate, or Intravenous glucose or glucagon injection without a test of plasma glucose.

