Patients will be instructed to measure finger-stick plasma glucose levels prior to the administration of carbohydrates whenever symptomatic hypoglycemia is suspected, unless safety considerations necessitate immediate glucose administration prior to confirmation, and then a glucose measurement should be performed as soon as safe, with appropriate diary documentation. Details on hypoglycemia episodes will be captured in the patient diaries, and patients will contact the sites as soon as possible following severe events to review the details and decide on any necessary measures to be taken.

Symptomatic hypoglycemia episodes will be documented on the dedicated hypoglycemia event page in the e-CRF. Symptomatic hypoglycemia events fulfilling the criteria of a SAE will also be documented on AE and SAE forms in the e-CRF.

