A listing of patients for all events reported on the dedicated eCRF “Symptomatic hypoglycemia” page will be provided and sorted by the following order: (1) patients with protocol defined symptomatic hypoglycemia including severe symptomatic hypoglycemia, documented symptomatic hypoglycemia, or probable symptomatic hypoglycemia (see [Section 2.1.4.1](#)); and (2) patients with symptomatic hypoglycemia not meeting protocol definition; and (3) patients with asymptomatic hypoglycemia.

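### A non-severe hypoglycemia event treated first and then measured above 70 mg/dL, as the protocol instructs, is neither documented nor probable and drops out of the summary tables

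*SAP*

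**What the plan says.** Protocol 10.6.1 asks patients to test before taking carbohydrate, "unless safety considerations necessitate immediate glucose administration prior to confirmation, and then a glucose measurement should be performed as soon as safe", and to record the episode in the diary. Under Protocol 9.2.1.2.3.1, glucose values from symptomatic episodes go into the patient's "diary and entered in the e-CRF", with no restriction to values taken before treatment.

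SAP 2.1.4.1 turns the definitions into e-CRF rules:

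- *Severe*: the patient could not self-treat and needed assistance, and had symptoms. No glucose value is required; the narrative notes that "Plasma glucose measurements may not be available during such an event".
- *Documented*: the patient treated himself or herself, or could have done so but was helped; symptoms; a measured value of 70 mg/dL or less.
- *Probable*: the same assistance answers; symptoms; a countermeasure; prompt improvement; and "with no plasma glucose value". The narrative says that "Probable symptomatic hypoglycemia is an event during which symptoms of hypoglycemia are not accompanied by a plasma glucose determination". The protocol's own wording is similar: "symptoms improved with oral carbohydrate, or Intravenous glucose or glucagon injection without a test of plasma glucose".

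SAP 2.4.5.1 restricts the summary of any symptomatic hypoglycemia, and the incidence rates, to events that meet one of these three definitions. The others go to a listing, in a group described as "patients with symptomatic hypoglycemia not meeting protocol definition".

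**The concern.** The protocol produces glucose values of two kinds. A value taken before treatment bears directly on whether the patient was hypoglycemic. A value taken after carbohydrate and recovery says little about glucose when the symptoms began. The SAP treats both alike. As a result, a patient who follows the instruction to measure afterwards can lose the event from the tables, while a patient who ignores it keeps the event as probable.

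Symptomatic hypoglycemia is a named safety endpoint. The trial compares a combination containing titrated insulin with a continued GLP-1 RA, and Protocol 9.6 itself expects some increase in hypoglycemia risk. The safety analysis is descriptive (SAP 2.4.5), so the tabulated counts and rates are what readers will rely on.

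**Working it through.** The plan states no hypoglycemia rate, so there is no figure to reproduce. The check applies the SAP rules to specimen events and follows the result into the tables.

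**Step 1. Classification.** Inputs are the SAP 2.1.4.1 conditions. Every specimen event has symptoms, a countermeasure and prompt improvement.

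| Glucose recorded (mg/dL) | Treated self, or able to but helped | Not able, needed assistance |
|---|---|---|
| none | probable | severe |
| 55 or 70 | documented | severe |
| 71 or 95 | no category | severe |

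The rules have no timing term, so the last row is the same whether the reading came before or after treatment. Excluding a pre-treatment 95 is reasonable. Excluding a post-treatment 95 is the defect. A post-treatment value of 70 or less still counts as documented.

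**Step 2. Destination.** Events with no category are outside the any-symptomatic and probable rows of SAP 2.4.5.1 and appear only in the listing. The adverse event tables do not recover them: Protocol 10.6.1 and Table 2 put symptomatic hypoglycemia on its dedicated page, and only events meeting SAE criteria also go on AE forms.

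**Step 3. Size, on assumed inputs.** Let *f* be the share of non-severe events treated first and tested afterwards, and *h* the share of those reading above 70 mg/dL. The share lost is L = f × h. Neither input is in the documents.

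- f = 5%, h = 50%: 0.05 × 0.5 = 2.5%
- f = 10%, h = 50%: 0.10 × 0.5 = 5%
- f = 30%, h = 80%: 0.30 × 0.8 = 24%
- f = 30%, h = 100%: 0.30 × 1.0 = 30%

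All lost events would otherwise be probable. The relative loss in that row is therefore larger than L whenever some events are documented.

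**Step 4. Between arms.** Write r_F and r_G for the true non-severe event rates and assume the same L in both arms. The tabulated difference is (r_F − r_G)(1 − L), smaller by the fraction L. The tabulated ratio is r_F(1 − L) / [r_G(1 − L)] = r_F / r_G, which is unchanged.

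**Step 5. Reach of a remedy.** Moving these events into probable changes the any-symptomatic and probable rows. It does not change the severe rows. Nor does it change the analyses that SAP 2.4.5.1 confines to documented events: subgroups, antibody status, weekly time course, time to first event, hour of day, and values below 60 mg/dL.

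**The case against.** The usual instruction, also given in the flow chart notes and Protocol 9.2.1.2.3.1, is to test before treating. Treating first is the exception, and only Protocol 10.6.1 asks for a later reading. Some of the episodes urgent enough to treat first will be severe and so remain counted. This limits the number of events at issue but does not remove the gap.

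The e-CRF page is not in the documents, and its glucose field may accept only a value at symptom onset. The narrative also speaks of symptoms accompanied by a determination, which a reading after recovery arguably does not satisfy. Either would close the gap if stated. Neither is stated, and the operative condition is simply "with no plasma glucose value".

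These episodes are also unconfirmed, and in an open-label trial symptom-only reporting may be influenced by knowing that the treatment contains insulin. That is a fair caution. It supports showing the added events visibly, and it argues against counting as probable every treated event with a value above 70 mg/dL, because some will have had a pre-treatment reading that contradicts hypoglycemia.

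A reader might infer that true events vanish from every count, rate and percentage, mainly in the FRC arm. The documents do not support that. Severe counts are intact, a patient with another qualifying event in the same category still counts in the percentages, and the omitted events are listed. No rates by arm are given.

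**Conclusion.** The gap is real but limited. It follows from the stated rules for non-severe events: testing as instructed can remove an event that would count if the patient did not test. It affects the any-symptomatic and probable counts and rates only.

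The size is unknown; the 2.5% to 30% range rests entirely on assumed shares. More lost events in the FRC arm is a reasonable inference, because that arm receives titrated insulin while control patients receive insulin only as rescue or for short-term use. It is not a documented fact. If it holds with equal loss fractions, the absolute excess is understated and the rate ratio is not. No hypothesis test or efficacy result is affected.

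**What to change.** Add one rule to SAP 2.1.4.1. An event whose only glucose value was taken after the countermeasure and is above 70 mg/dL is treated as having no plasma glucose determination, and is probable if the symptom, countermeasure and recovery conditions hold. Events with a pre-countermeasure value above 70 mg/dL stay excluded.

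Where the order of measurement and treatment cannot be recovered from the e-CRF, diary or meter download, show the affected events by arm in a separate row or sensitivity table, without merging them into probable. If the e-CRF field already takes only pre-countermeasure values, saying so in the SAP settles the point.

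The cost is one sentence and a derivation from recorded times, or one extra table. The downside is that a few unconfirmed episodes enter the probable category in an open-label trial; giving them their own row keeps this visible.

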2.1.4.2 Adverse events variables

Adverse event observation period

- Pre-treatment adverse events are AEs that developed or worsened or became serious from the signed informed consent date up to first injection of open-label IMP.
- Treatment-emergent adverse events are AEs that developed or worsened (according to the Investigator’s opinion) or became serious during the period from the administration of first dose of the study treatment up to 3 days (9 days for the weekly GLP1) after the last administration.
- Post-treatment adverse events are AEs that developed or worsened or became serious during the post-treatment period.

All AEs (including SAEs and AEs with prespecified monitoring) will be coded to a lower-level term (LLT), preferred term (PT), high-level term (HLT), high-level group term (HLGT), and associated primary system organ class (SOC) using the version of Medical Dictionary for Regulatory Activities (MedDRA) currently in effect at Sanofi at the time of database lock.

Record the occurrence of AEs (including SAEs and AEs with prespecified monitoring) from the time of signed informed consent until the end of the study.

AESI, AE requiring specific monitoring, or specific AEs to be analyzed:

- Local tolerability at injection site: identified by searching the term “injection site” in either the PTs coded from the investigator reported terms or the PTs coded from the Allergic Reaction Assessment Committee (ARAC) diagnosis terms.
- Allergic or allergic-like reactions: events recorded on the AE form for “suspected allergic reaction” and its associated complementary forms. Allergic reaction or possible allergic reaction will be adjudicated by the ARAC.
- Increased pancreatic enzymes > 2 x ULN/suspected pancreatitis: all events confirmed by a repeated test recorded on the AE form for “increased lipase and/or amylase greater than 2 x

ULN” and its associated complementary forms. All events reported will be sent to Pancreatic Safety Assessment Committee (PSAC) for adjudication of pancreatitis.

- Pancreatic neoplasm: All pancreatic neoplasm related events (AEs of pancreas carcinoma, AEs of pancreas neoplasm benign or malignant AEs of pancreas neoplasm unspecified, AEs of pancreatic endocrine neoplasm/carcinoma, or AEs of pancreas mass, cyst, pseudocysts) will be reviewed, assessed and adjudicated by the PSAC for pancreatic neoplasm.
- Increased calcitonin ≥ 20 pg/mL: events recorded on the AE form for “increased calcitonin” and its associated complementary form.
- Increased ALT: events recorded on the AE form for “ALT increase” and its associated complementary form.
- Device related events reported on eCRF “Device-related events questionnaire”.

Pregnancy and overdose are included in overall AE summaries if any.

2.1.4.3 Deaths

The deaths observation period are per the observation periods defined above.

- Death on-study: deaths occurring during the on-study observation period
- Death on-treatment: deaths occurring during the on-treatment period
- Death post-study: deaths occurring after the end of the study

2.1.4.4 Laboratory safety variables

Clinical laboratory data consists of blood analysis (including hematology and clinical chemistry) and urinalysis (albumin/creatinine ratio). Clinical laboratory values will be summarized in both standard international units and conventional units.

The laboratory data will be collected at designated visits (see study flowchart in [Appendix D](#). The following laboratory data will be measured at a central laboratory and used as safety endpoints:

- Hematology
 - Red blood cells, platelets: hemoglobin, hematocrit, red blood cells (erythrocytes) count, platelets count.
 - White blood cells: white blood cells count, and differential counts (neutrophils, lymphocytes, monocytes, basophils, and eosinophils).
- Clinical chemistry
 - Lipid parameters: total cholesterol, high density lipoprotein (HDL) cholesterol, low density lipoprotein (LDL) cholesterol, triglycerides.
 - Pancreatic enzymes: lipase, amylase.

- Serum calcitonin.
- Electrolytes: sodium, potassium, calcium, phosphorus.
- Renal function: creatinine, calculated creatinine clearance, uric acid.
- Liver function: alanine aminotransferases (ALT), aspartate aminotransferases (AST), alkaline phosphatase (ALP), total bilirubin (and, in case of values above the normal range, differentiation in conjugated and non-conjugated bilirubin).
- Urine analysis: albumin/creatinine ratio.

For triglycerides, only values assessed in fasted patients will be analyzed.

Other laboratory data not mentioned above (pregnancy test, serum follicle-stimulating hormone [FSH], hepatitis screen, and urinalysis) will not be defined as safety endpoints (collected at screening only as per study flowchart in [Appendix D](#), except for pregnancy test which is also performed during study).

Technical formulas are described in [Section 2.5.1](#).

2.1.4.5 Vital signs variables

Vital signs include supine heart rate (bpm) and systolic and diastolic blood pressures (mmHg) in seated position.

2.1.4.6 Physical examination

Any abnormality related to physical examination will be reported in the eCRF “Adverse Event” page.

2.1.4.7 Electrocardiogram variables

ECGs are measured automatically by the device from the investigator as automatic 12-lead ECG. ECG status of “normal” or “abnormal” will be reported in the eCRF as determined by the Investigator.

2.1.4.8 Immunogenicity variables

Antibody variables in FRC group:

- Anti-insulin glargine antibody:
 - Status (Positive, Negative) and titer;
 - Cross-reactivity of anti-insulin glargine antibodies with human insulin.
- Anti-lixisenatide antibody:
 - Status (Positive, Negative) and concentration;

- Cross-reactivity of anti-lixisenatide antibodies with GLP-1 and glucagon as well as neutralizing effects of these antibodies against lixisenatide, GLP-1 and glucagon.

The on-treatment period for antibody variables is defined as the time from the first injection of open-label IMP up to 28 days after the last injection of open-label IMP.

2.1.5 Pharmacokinetic variables

Pharmacokinetics variables include total plasma concentrations of lixisenatide for FRC group.

